- Prevention of stroke and systemic embolism in adult patients with non-valvular atrial fibrillation with one or more risk factors, such as congestive heart failure, hypertension, aged ≥ 75 years, diabetes mellitus, and prior stroke or transient ischaemic attack.
- Treatment of DVT and prevention of recurrent DVT and PE following an acute DVT in adults.

As a part of this safety risk management plan revision, a physician educational pack has been developed that includes the summary of product characteristics, prescriber guide (Appendix A), and patient alert card (Appendix B), with the aim to increase awareness and understanding among physicians and patients about the potential bleeding risk during treatment with rivaroxaban.

The prescriber guide covers the following topics:

- Switching from or to rivaroxaban treatment
- Necessity of taking the 15-mg and 20-mg tablets with food
- Management of overdose situations
- Use of coagulation tests and their interpretation
- Dosing recommendations
- Perioperative management
- Populations at higher risk of bleeding
- Necessity of providing all patients with a patient alert card and counselling about the details of the patient alert card

The patient alert card contains the following key safety messages:

- Signs or symptoms of bleeding and when to seek attention from a health care provider
- Importance of treatment compliance
- Necessity of taking the 15-mg and 20-mg tablets with food
- Necessity of carrying the patient alert card with them at all times
- Necessity of informing health care professionals (HCPs) that they are taking rivaroxaban if they need to have any surgery or invasive procedure

This protocol describes the planned evaluation of these elements of the risk management plan. Evaluations are planned for administration at 18 months, 3 years, and 7 years post-launch. The status of these assessments will be presented regularly in periodic safety update reports. The five countries to be included in the study are the United Kingdom (UK), Germany, France, Italy, and Spain. Due to drug approval delays in Italy, the 18-month assessment will not include Italy. Therefore, data will be collected from four countries in the 18-month assessment (UK, Germany, France, and Spain).

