2 SPECIFIC AIMS

The primary objective of this cross-sectional epidemiologic study is to measure physician and patient awareness and understanding of the key messages in the prescriber guide and patient alert card.

Specifically, the following objectives will be addressed:

- Investigate whether physicians and their patients have received the educational materials.
- Assess knowledge and understanding among physicians regarding key safety information contained in the prescriber guide and assess how physicians use the materials in their daily practice.
- Assess knowledge and understanding of patients regarding the key safety information contained in the patient alert card and determine if the patients use and carry the patient alert card with them.

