3.1.5 Physician Questionnaire Development

Standard survey methodologic principles have been used to develop the physician questionnaire, which will assess physicians' knowledge of the following concepts as outlined in the prescriber guide and educational materials:

- Switching from or to rivaroxaban treatment
- Necessity of taking the 15-mg and 20-mg tablets with food
- Use of coagulation tests and their interpretation
- Dosing recommendations
- Perioperative management
- Populations at higher risk of bleeding
- Necessity of providing all patients with a patient alert card and counselling about the details of the patient alert card

Physicians will be asked about their receipt and use of the prescriber guide (Appendix A) as well as counselling of patients and distribution of the patient alert card. In addition, physicians will be asked to characterise their practice in terms of years in practice, size of practice, and history of treating patients with the diagnoses of interest. Other characteristics will be collected to facilitate stratified analyses to explore factors associated with knowledge and behaviour. The physician questionnaire is designed to take 10-15 minutes to complete. The physician questionnaire has been cognitively tested with physicians in each of the target countries. Section 3.3 provides a detailed description of the cognitive pretesting process. Modifications have been made to the questionnaire based on the pretesting results and additional feedback from the sponsor. The final version of the questionnaire can be found in Appendix C. Some modifications to the questionnaire are anticipated based on country-specific requirements.

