[IF Q1 = "I have not prescribed Xarelto for this indication", SKIP TO intro text preceding Q18.]

The following questions are about the indication for prevention of stroke and systemic embolism in patients with non-valvular atrial fibrillation.

Q16. What is the standard recommended dose of Xarelto for the prevention of stroke and systemic embolism in patients with non-valvular atrial fibrillation?

(Tick one.)

- 20 mg taken once a day
- 15 mg taken once a day
- 10 mg taken once a day
- None of the above
- I don't know

Q17. What is the recommended dose for patients with moderate or severe renal impairment (creatinine clearance of 15-49 mL/min) receiving Xarelto for the prevention of stroke and systemic embolism in patients with non-valvular atrial fibrillation?

(Tick one.)

- 20 mg taken once a day
- 15 mg taken once a day
- 10 mg taken once a day
- None of the above
- I don't know

[IF Q2 = "I have not prescribed Xarelto for this indication", SKIP TO intro text preceding Q19.]

The following questions are about the indication for deep vein thrombosis treatment and secondary prevention in adult patients.

Q18. What is the standard recommended dose for patients receiving Xarelto for deep vein thrombosis treatment and secondary prevention?

(Tick one.)

- 20 mg twice a day for the first three weeks of administration, followed by 20 mg taken once a day
- 15 mg twice a day for the first three weeks of administration, followed by 20 mg taken once a day
- 10 mg once a day
- None of the above
- I don't know

In this next section, please tell us about any information you have received about Xarelto.

Q19. From which of the following sources did you receive information about Xarelto?

(Tick all that apply.)

- Xarelto Prescriber Guide
- Briefing from a company representative
- Discussion with a clinical expert
- The Summary of Product Characteristics for Xarelto
- Clinical trials published in the medical literature
- Other
- None of the above

Q20. How helpful were these sources to you in treating and educating your patients?

[ONLY DISPLAY RESPONSES THAT WERE CHECKED IN Q19; IF Q19 = “NONE OF THE ABOVE”, SKIP TO Q21.]

| | 1 Not at all helpful | 2 | 3 | 4 | 5 Extremely helpful |
|--|-------------------------------------|--------------------------|--------------------------|--------------------------|------------------------------------|

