| Xarelto Prescriber Guide |  |  |  |  |  |
| Briefing from a company representative |  |  |  |  |  |
| Discussion with a clinical expert |  |  |  |  |  |
| Summary of Product Characteristics |  |  |  |  |  |
| Medical Publications |  |  |  |  |  |
| Other |  |  |  |  |  |

Q21. Have you received Xarelto Patient Alert Cards to provide to your patients?

- Yes
- No

[IF Q21 IS NO, SKIP TO Q23.]

Q22. Considering the Xarelto patients under your care, to how many did you provide a Patient Alert Card?

- Every one of my patients
- Most of my patients
- A few of my patients
- None of my patients

Q23. When would you discuss the information on the Patient Alert Card with your patients taking Xarelto?

(Tick all that apply.)

- When first prescribing Xarelto
- When a patient is facing an invasive procedure or surgical intervention
- When a patient has bleeding complications
- When a patient has a Xarelto related adverse event
- I do not use the Patient Alert Card
- Other

In this next section, please tell us a little about yourself and your clinical practice.

Q24. Which of the following best describes your specialty?

- General medicine
- Neurology
- Cardiology
- Haematology
- Accident & Emergency medicine
- Oncology
- Other

Q25. How many years have you been practicing medicine?

- 5 years or less
- 6 to 10 years
- 11 to 15 years
- 16 to 20 years
- 21 to 25 years
- More than 25 years

Q26. Are you...?

- Male
- Female

Q27. How would you characterise your practice?

(Tick all that apply.)

- General practice
- Hospital-based clinic
- Nursing home
- Other

0302949 Physician Questionnaire

Thank you for completing the questionnaire!

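### The physician questionnaire measures receipt and use of the prescriber guide only indirectly, although Section 3.1.5 says physicians will be asked about both

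*Protocol*

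**What the plan says.** Protocol Section 2 lists two objectives that concern the materials themselves: "Investigate whether physicians and their patients have received the educational materials" and, alongside physician knowledge, "assess how physicians use the materials in their daily practice". Section 1 defines those materials: "a physician educational pack has been developed that includes the summary of product characteristics, prescriber guide (Appendix A), and patient alert card (Appendix B").

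Section 3.1.5 narrows this to the guide: "Physicians will be asked about their receipt and use of the prescriber guide (Appendix A"), together with counselling and alert-card distribution. Sections 3.1.1 and 3.1.2 describe the questionnaire in similar terms, and Section 5 says this part of the study will show how physicians use the materials.

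Section 3.1.5 refers to Appendix C as the final questionnaire. Apart from the introductory text, the guide appears there in three places:

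- Q19, as the first option in a tick-all list: "Q19. From which of the following sources did you receive information about Xarelto".
- Q20, "Q20. How helpful were these sources to you in treating and educating your patients", with the programming rule "ONLY DISPLAY RESPONSES THAT WERE CHECKED IN Q19".
- A link to the guide after the last question.

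The alert card has its own receipt item, "Q21. Have you received Xarelto Patient Alert Cards to provide to your patients". Q22 then asks how many patients were given it, and Q23 asks when it is discussed, with an option for not using it.

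**The concern.** The text of the protocol promises a measurement that the instrument makes only by proxy. Q19 asks where information came from. That is related to whether the guide arrived, but it is not the same question. Q20 asks how helpful the guide was, and perceived helpfulness is not use.

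The distinction matters because the study evaluates a risk-minimisation tool. If guides are not reaching prescribers, distribution needs attention. If they arrive and are not read or used, the guide itself needs attention. Q19 merges these two situations. An analysis plan cannot repair this later, because it cannot analyse questions that were never asked. Assessments are planned at 18 months, 3 years and 7 years, so the gap could carry through each one if the questionnaire is reused.

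**Working it through.** **Step 1. Match each promised measurement to its items** (Section 2, Section 3.1.5, Appendices C and D).

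| Promised measurement | Item | Direct? |
|---|---|---|
| Physician received the guide | Q19, one tick option | No |
| Physician read the guide | none | – |
| Physician uses the guide in practice | Q20 helpfulness, only if ticked in Q19 | No |
| Physician received alert cards | Q21 | Yes |
| Physician distributes and discusses the card | Q22, Q23 | Yes |
| Patient received the card | Patient Questionnaire #2, Q10 | Yes |
| Patient read, carries and shows the card, or had it explained | Patient Questionnaire #2, Q11 to Q15 | Yes |

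The direct format was available and was used for the card. Only the guide lacks it.

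**Step 2. What an unticked guide box in Q19 can mean.** It can mean that the guide was (a) not received, (b) received but unread, (c) received but not recalled, or (d) received but not regarded as a source of information. There is no option for not remembering. The SmPC comes in the same pack and is a separate option in Q19, so a recipient who read only the SmPC could tick that box alone. Q20 adds nothing here, because it is hidden from everyone who left the guide unticked.

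**Step 3. Why the receipt figure is not identified.** Let R be true receipt and u the share of recipients who tick the guide. If no non-recipient ticks it, Q19 estimates R × u. The documents give neither R nor u, so the values below are assumptions for illustration.

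| Assumed R | u = 0.5 | u = 0.7 | u = 0.9 | u = 1.0 |
|---|---|---|---|---|
| 60% | 30% | 42% | 54% | 60% |
| 80% | 40% | 56% | 72% | 80% |
| 95% | 47.5% | 66.5% | 85.5% | 95% |

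At R = 80% the understatement runs from 80 − 40 = 40 points to 80 − 80 = 0 points. Read the other way, an observed 56% fits R = 80% with u = 0.70. It also fits R = 60% with u = 0.56/0.60 = 0.93, and R = 56% with u = 1. Nothing in the questionnaire tells these apart. If a share v of non-recipients also tick the guide, Q19 estimates R × u + (1 − R) × v, and the error need not even be an understatement.

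**Step 4. Precision, for background.** Exact (Clopper-Pearson) limits reproduce the rows of Table 1 that were checked: 85% correct gives 80.4% to 88.8% at n = 300 and 83.1% to 86.8% at n = 1,500. These figures stand. A larger sample narrows the interval around R × u, not around R.

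**The case against.** The strongest reply is that Q19 works as a receipt question. Its lead-in asks about information the physician has received, its stem uses the same verb, all applicable options may be ticked, and the guide is listed first. It does not ask for the main source. Patient Questionnaire #1 shows how the authors word that when they want it: its Q6 asks where most of the information came from and allows one answer. Many recipients may well tick the guide. This stands, and it rules out asserting that a physician who relied on the SmPC would leave the guide unticked. It does not remove the ambiguity of an unticked box.

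A reader might infer that the first objective and half of the second cannot be answered at all. The documents do not support that. Both objectives in Section 2 refer to the educational materials, which include the alert card, and receipt and use of the card are asked directly of physicians and patients. For the guide, Q19 is a proxy for receipt, and Q20, which refers to treating and educating patients, is a weak proxy for use.

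A reader might also attach a definite bias to Q19. Any such figure comes from assumed inputs, and the simple product R × u has understatement built in. If every recipient ticks, it is zero.

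Nor is guide receipt a prespecified stratifier: for physicians, Section 4 names country, speciality and other logical variables. The primary objective, awareness and understanding of key messages, rests on the knowledge items, which are untouched.

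**Conclusion.** The point holds in a limited form. Section 3.1.5 promises data on receipt and use of the prescriber guide, and Appendix C supplies only proxies. Guide receipt is not cleanly estimable, and guide use in daily practice is not directly measured.

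The size of any error cannot be derived from the documents. The illustrative 0 to 40 points rests on an assumed 80% receipt, ticking by 50% to 100% of recipients, and no ticks by non-recipients. No sample size, precision figure or named analysis in the protocol changes, and the physician knowledge items (Q5 to Q18) are unaffected. The change is worth making because it is inexpensive, bears on a stated objective, and cannot be made up for after fielding.

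**What to change.** After the knowledge block (Q5 to Q18) and before Q19, add:

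1. *Have you received the Xarelto Prescriber Guide?* Yes / No / Don't remember. This parallels Q21.
2. If yes, one closed item on whether it was read, for example fully, partly or not at all.
3. If yes, one closed item on how it is used in practice, with response options to be settled in pretesting.

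Report item 1 as the measure of guide receipt, and keep Q19 and Q20 unchanged as the measure of information sources. Section 3.1.6 does not let respondents return to earlier questions, so items in this position cannot alter the knowledge answers already given.

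The cost is about a minute added to a 10 to 15 minute questionnaire, translation, brief pretesting (the existing form was cognitively tested with 25 physicians, and new items would otherwise be untested), and ethics review of the amended questionnaire. Naming the guide just before Q19 may also prompt more ticks there, so Q19 results before and after the change should be compared with care. The new items remain self-report and depend on recall, which is why the third response option is needed.

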 **Xarelto**
rivaroxaban

Prescribing Information can be found on pages 10 and 11

211 mm

DO NOT PRINT GUIDES

297 mm

Bayer HealthCare have designed this educational pack to support you in the appropriate prescribing of Xarelto. It contains important information specifically relating to 15mg and 20mg dosing of Xarelto, for use in stroke prevention in AF and treatment of DVT and PE.

Within this pack you will find a:

- Prescriber guide
- Summary of product characteristics (SmPC)
- Patient alert card

If you would like to order more copies of the Xarelto educational pack, please visit www.xarelto-info.co.uk

Alternatively, please contact Bayer Medical Information at [contact] or call [name].

DO NOT PRINT GUIDES

211 mm

**NOW UPDATED
AND INCLUDES A
NEW INDICATION**

XARELTO® (RIVAROXABAN)

PRESCRIBER GUIDE

FOR 15MG AND 20MG DOSING

Prescribing information can be found
on pages 10 and 11

This guide is to be used to support the appropriate use of Xarelto in eligible atrial fibrillation (AF) patients and for the treatment of deep vein thrombosis (DVT) and pulmonary embolism (PE).

It includes the following information:

- **Indications**
- **Dosing recommendations**
- **Populations potentially at higher risk of bleeding**
- **Perioperative management**
- **Overdose**
- **How to manage bleeding complications**
- **Coagulation testing**

Xarelto patient alert card

You must provide a patient alert card to each patient who is prescribed Xarelto 15mg or 20mg.

Please explain the implications of anticoagulant treatment to patients, in particular highlighting the need for:

- treatment compliance
- taking medication with food
- signs or symptoms of bleeding
- when to seek medical attention.

The patient alert card will inform treating physicians and dentists about the patient's anticoagulation treatment and will contain emergency contact information.

Please instruct patients to carry the patient alert card with them at all times and present it to every health care provider.

INDICATIONS

Prevention of stroke and systemic embolism in adult patients with non-valvular AF with one or more risk factors, such as congestive heart failure, hypertension, age \geq 75 years, diabetes mellitus, prior stroke or transient ischaemic attack.

Treatment of DVT and PE and prevention of recurrent DVT and PE in adults. (See section 4.4 of the SmPC for haemodynamically unstable PE patients).

DOSING RECOMMENDATIONS

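### Physician questionnaire Q22 has no answer between most and a few patients and no don't-know option, so partial distribution of the alert card may be misclassified by an unknown amount

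*Protocol*

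**What the plan says.** Protocol section 3.1.5 says physicians will be asked about "counselling of patients and distribution of the patient alert card". Appendix C does this in three items. Q21 asks whether the physician has received cards. Q22 asks, "Considering the Xarelto patients under your care, to how many did you provide a Patient Alert Card", and offers "Every one of my patients", "Most of my patients", "A few of my patients" and "None of my patients". Q23 asks when the card is discussed. Physicians without cards do not see Q22: "IF Q21 IS NO, SKIP TO Q23".

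Section 3.1.6 makes the form closed-ended, and earlier answers cannot be revised. The standard for distribution is set by the prescriber guide in Appendix A: "You must provide a patient alert card to each patient who is prescribed Xarelto 15mg or 20mg".

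On the patient side, section 3.2.5 lists receipt of the card as a measured concept, and Q10 of Patient Questionnaire #2 (Appendix D) asks each patient whether a card had been received before that day.

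**The concern.** The scale mixes shares and counts. Its top, second and bottom options read as shares of the physician's patients, while "A few of my patients" reads as a small number of people. No option carries a definition or a percentage. A physician with a sizeable caseload who gives the card to, say, a third of patients has not given it to most of them, and has given it to more than a few.

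Such a physician must choose a neighbouring option, and may lean towards the more creditable one. There is no way to say that the share is unknown. The questionnaire is more careful elsewhere: Q5 to Q18 all carry a don't-know option, Q19 and Q23 carry an *Other*, and Q13 of Patient Questionnaire #2 uses a scale with no gap (all, some or none of the time, or don't know).

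What is at stake is the grading of partial distribution on a named physician topic. No analysis plan can recover it, because the information is never collected. Section 1 plans assessments at 18 months, 3 years and 7 years, so a scale changed after the first round would also break comparability over time.

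**Working it through.** The protocol states no figure for Q22, so there is none to reproduce. The check is a reading of the scale, followed by a bound on its possible effect.

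**1. Do the options cover every case?** Section 3.1.2 requires only one rivaroxaban patient in the past 6 months, and the lowest volume band in Q1 and Q2 is 1 to 10. The cases below are illustrative.

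| Cards given / patients | Share | Fitting option in Q22 |
|---|---|---|
| 16 / 40 | 40% | none |
| 3 / 8 | 37.5% | "A few of my patients", read as a count |
| 3 / 5 | 60% | "Most of my patients" by share, and "A few of my patients" by count |
| 22 / 40 | 55% | "Most of my patients" |

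The gap lies mainly below one half and mainly among physicians with more than a handful of patients. With small caseloads the problem is more one of overlap than of a gap.

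**2. Which results are touched?** A physician who gave the card to all patients, or to none, has an exact answer. Only the split between the two middle options is uncertain.

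**3. How far could it move a summary?** Let m be the share of Q22 respondents in the gap and b the percentage in the two upper options if all of them tick "A few of my patients". If all of them tick "Most of my patients" instead, the percentage becomes b + m. Neither b nor m is in the documents. Assuming b = 60%:

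- m = 5%: 60% to 65%
- m = 10%: 60% to 70%
- m = 20%: 60% to 80%

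**4. Comparison with sampling precision.** Exact (Clopper-Pearson) limits reproduce every row of Table 1 in section 3.1.4; for example, n = 300 at 85% gives 80.4% to 88.8%. The same method at 60% gives:

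| n | 95% limits | Half-width (points) |
|---|---|---|
| 300 (one country) | 54.2% to 65.6% | (65.6 − 54.2)/2 = 5.7 |
| 1,200 (18-month round) | 57.2% to 62.8% | (62.8 − 57.2)/2 = 2.8 |
| 1,500 (five countries) | 57.5% to 62.5% | (62.5 − 57.5)/2 = 2.5 |

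So the largest possible shift exceeds sampling error when m is above about 2.5% in the five-country total, or above about 6% in one country. Both comparisons use the full target n. The real Q22 denominator is smaller because physicians without cards skip the item, so the half-widths would be somewhat wider.

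Step 3 is a bound only: it returns the assumed m as the largest shift, reached if every physician in the gap rounds the same way.

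**The case against.** Several points on the other side are sound.

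- **Q22 is not the study's only measure of card receipt.** A reader might infer that it is, but Q10 of Patient Questionnaire #2 asks patients directly. That item is not a full substitute: it rests on recall, targets about 100 patients per country, and draws on practices excluded from the physician assessment (section 3.2.3). It does mean that the receipt objective does not hang on Q22.
- **No two-way split is specified.** The protocol nowhere combines the upper two options against the lower two. Section 4 promises frequencies and percentages for categorical data, which would show all four options. Since the guide requires a card for each patient, the most direct compliance figure is the percentage answering "Every one of my patients", and the gap does not touch it.
- **The middle of the range is not wholly uncovered.** A share just above one half fits "Most of my patients", and a physician with few patients can often answer "A few of my patients" truthfully.
- **The questionnaire was pretested.** Section 3.3 reports cognitive testing with 25 physicians across five countries, intended among other things to find faults in response choices. This carries some weight, but no result for Q22 is reported and the gap remains in the final version.

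These points limit the consequence. They do not close the gap in the scale.

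**Conclusion.** The point holds as a minor flaw in questionnaire design. Q22 does not grade partial distribution reliably, chiefly for shares below one half among physicians with more than a handful of patients. The percentages at the two ends of the scale stand.

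The size is unknown. A reader might go further and infer that the distribution result is misclassified as a matter of fact, or is off by some stated number of points. The documents support neither: they give no information on how many physicians fall in the gap or which way they would round. The 5% to 20% used above is an assumption chosen to show scale. The conclusion rests on the ordinary meaning of the undefined option words and on the closed form of the item.

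**What to change.** Before fielding, replace the Q22 options with:

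- *All of my patients*
- *More than half, but not all*
- *Half or fewer, but at least one*
- *None*
- *I don't know*

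In terms of the share given the card, the four substantive options cover 100%; above 50% and below 100%; above 0% and up to 50%; and 0%. They leave no gap and do not overlap, and they work for any caseload: 16 of 40, 3 of 8 and 1 of 2 fall in the third option, and 3 of 5 in the second. Narrow percentage bands would serve small caseloads worse, since one card among five patients is already 20%.

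The cost is one more response option (five instead of four) and a minor translation and ethics update to an item that has already been pretested. The third option does not separate a few patients from nearly half. The same wording should then be kept for all three assessments.
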